## 17.2 Sample Size/ Accrual Rate

The sample size estimation was completed using the log-rank test. A total sample size of 106 (n=53 in each arm) provides 80% power to detect a 1.5 month improvement in the median PFS, i.e. 2.9 months vs. 4.4 months, with a one-sided significance level equal to .10 (type I error). This estimation is based on the assumptions that accrual time is 24 months, additional follow-up time is 12 months, and the ratio randomization is 1:1.

## 17.3 Analysis of Secondary and Exploratory Endpoints

We will calculate the ORR, CBR, DOR, and OS and corresponding 95% confidence intervals. PFS, ORR, and DOR will also be analyzed using irRECIST.

RNA-seq will be performed on all biopsies to assign a triple negative subtype, to determine baseline and treatment-induced changes in GE after therapy and define mutations present in the tumors both at baseline and upon progression of the disease. We expect an enrichment of drug resistance-associated mutations/gene amplifications particularly in tumors that regress and later recur while on therapy. Somatic SNPs and structural variants will be validated by whole exome sequencing (WES) of genomic DNA from the tumor and matched blood. We will validate mutations by targeted capture approaches that allow high-level coverage (greater than 200X) and analysis of clonality. The status of p53, BRCA1/2, PIK3CA, PTEN, INPP4B and other mutations associated with TNBC, along with PDL1 expression and TILs in the tumor tissue is critical for testing our hypothesis. We anticipate significant opportunity for discovery of novel mutations as well as those arising from selection during resistance to the therapies under investigation. Statistics on the correlative endpoints (tissue assays) will be primarily descriptive. Therefore, these studies are considered to be exploratory and potentially hypothesis-generating.

Regarding the impact of body composition on immune phenotype and prognosis in patients receiving PDL1 blockade for metastatic triple negative breast cancer in this study, data analysis will be primarily exploratory. Pearson's rho will be used to estimate the correlation between low muscle mass (sarcopenia) and T cell exhaustion (PD1 and CTLA4 expression). Additional exploratory analysis will include the linear regression model to adjust for the potential confounders such as age and gender. It is anticipated this study would provide data from 106 patients. Assuming about 10% may not be able to provide evaluable data, we will have the complete data from 95 patients. A sample size of 95 would have 84.7% power to detect a true correlation  $\rho=0.3$  versus the null hypothesis  $\rho=0$ , with a type-I error of 0.05. To evaluate the impact of body composition on prognosis by progression free survival in patients receiving immunotherapy, we will evaluate only the study cohort receiving atezolizumab (n = 53). A Cox regression will be used to investigate the association between low muscle mass and PFS, while including T cell exhaustion (PD1 and CTLA4 expression) as the additional covariates as well as other potential confounders.

## 17.4 Statistical Analysis Plan

Demographic information, such as age and race, will be tabulated. Descriptive statistics, including means, standard deviations, and ranges for continuous parameters, as well as percents and frequencies for categorical parameters, will be presented. Investigation for outliers and assumptions for statistical analysis, e.g., normality and homoscedasticity, will be made. If necessary, data will be

transformed by utilizing appropriate transformations such as log or square root. Adverse medical events will be tabulated. NCI toxicity Grade 3 and Grade 4, and laboratory abnormalities will be listed.

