## **12. MEASUREMENT OF EFFECT**

For the purposes of this study, patients should be re-evaluated for response after every 3 cycles. Response and progression will be evaluated in this study using the international criteria proposed by the revised Response Evaluation Criteria in Solid Tumors (RECIST) Committee (version 1.1). Any evaluable or measurable disease must be documented at screening and reassessed at each subsequent tumor evaluation. For PFS analysis, patients will be considered to have disease progression if their tumor assessment shows PD by RECIST. However, as conventional response

criteria may not adequately assess the activity of immunotherapeutic agents because radiographic progressive disease does not necessarily reflect therapeutic failure, for patients on the carboplatin + atezolizumab arm, if a patient is found to have disease progression by RECIST, at the discretion of the treating physician, the patient may remain on study and managed by irRECIST (see section 12.5) provided he/she meets the following criteria:

- Evidence of clinical benefit as assessed by the investigator.
- Absence of symptoms and signs (including worsening laboratory values [e.g., new or worsening hypercalcemia]) indicating clinically significant progression of disease
- No decline in ECOG performance status that can be attributed to disease progression
- Absence of tumor progression at critical anatomical sites (e.g., leptomeningeal disease) and no other signs/symptoms of unequivocal disease progression. This includes tumor progression that cannot be managed by protocol-allowed medical interventions (ie., pain secondary to disease or unmanageable ascites, etc.), as determined by the investigator after an integrated review of radiographic data and clinical status.

Scans should be repeated after 6 weeks, and if progression is confirmed by irRECIST, the patient should be removed from study. If scans by irRECIST show the patient to not have disease progression, the patient may remain on study after discussion with the Protocol Chair. Patients on the carboplatin alone arm who show progression by RECIST must either be removed from study or cross over to receive atezolizumab.

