#### **13.1 General**

Adverse event collection and reporting is a routine part of every clinical trial. This study will use the descriptions and grading scales found in the NCI Common Terminology Criteria for Adverse Events version 5.0 (CTCAE v.5.0) that is available at <http://ctep.cancer.gov/reporting//ctc.html>.

Information on all adverse events, whether reported by the participant, directly observed, or detected by physical examination, laboratory test or other means, will be collected, recorded, followed and reported as described in the following sections.

Adverse events experienced by participants will be collected and reported from initiation of study medication, throughout the study, and within 30 days of the last dose of study medication. Participants who experience an ongoing adverse event related to a study procedure and/or study medication beyond 30 days will continue to be contacted by a member of the study team until the event is resolved, stabilized, or determined to be irreversible by the participating investigator.

Participants should be instructed to report any serious post-study event(s) that might reasonably be related to participation in this study. The investigator should notify the IRB and any other applicable regulatory agency of any unanticipated death or adverse event occurring after a participant has discontinued or terminated study participation that may reasonably be related to the study.

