## **17. STATISTICAL CONSIDERATIONS**

### **17.1 Study Design/ Endpoints**

The primary endpoint of this trial is the median PFS of carboplatin + atezolizumab versus carboplatin alone in patients with metastatic triple negative (ER/PR/HER2 negative) breast cancer. Prior studies have shown a median progression free survival of 2.9 months in patients with triple negative breast cancer receiving cisplatin or carboplatin who have received up to one prior chemotherapy regimen and a stable disease rate of approximately 5% at 6 months. We therefore propose that an improvement in median PFS of 2.9 months for single agent carboplatin to 4.4 months for the combination of carboplatin with atezolizumab would render this therapy worthy of further study. The overall PFS data will be estimated using the Kaplan-Meier method with 95% confidence intervals.

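### Section 17.4 tabulates adverse events with no allowance for time at risk, although the design assumes that the combination arm is treated, and so observed, for longer

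*Combined protocol and SAP*

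**What the plan says.** Section 17.4 states: "Adverse medical events will be tabulated. NCI toxicity Grade 3 and Grade 4, and laboratory abnormalities will be listed". For categorical data in general the same section prescribes "percents and frequencies for categorical parameters", so a table of n (%) is the natural reading. No patient-time denominator, exposure-adjusted rate, time-to-event method, fixed window or summary of treatment duration is given. The column in which events after crossover are counted is not stated either.

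Section 13.1 has adverse events "collected and reported from initiation of study medication, throughout the study, and within 30 days of the last dose of study medication". Section 8.5 continues treatment until a removal criterion in Section 8.7 applies, chiefly progression or intolerable toxicity. Section 17.1 takes as its target an "improvement in median PFS of 2.9 months for single agent carboplatin to 4.4 months for the combination".

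Several rules make exposure depend on the arm:

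- Section 12 says, for combination patients with RECIST progression, that "at the discretion of the treating physician, the patient may remain on study and managed by irRECIST". Control patients with RECIST progression must leave the study or cross over. Section 2, by contrast, says that combination patients stop study drugs at RECIST progression; the two passages must be reconciled.
- Section 8.7 lets combination patients continue on one drug after toxicity to the other.
- Section 8.1 lets carboplatin be stopped after cycle 6 in the combination arm, with atezolizumab continued.
- The study calendars (Sections 7.1 and 7.2) also place surveillance for adverse events of special interest (AESIs) at the 1-, 2- and 3-year follow-up.

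**The concern.** A crude percentage of patients with an event depends on how often events occur per month and on how many months the patient is watched. Here the second factor depends on efficacy: the longer the combination holds off progression, the longer its patients are treated and observed. A between-arm comparison of crude percentages therefore mixes toxicity with duration, most strongly when the treatment works as hypothesised. Section 8.1 says that the trial evaluates the safety profile of carboplatin with or without atezolizumab, and the crude table alone cannot separate the two explanations.

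**Working it through.** **The plan's own figure.** The hazard ratio is 2.9/4.4 = 0.659. By Schoenfeld's formula at one-sided 0.10 and 80% power, events = 4 × (1.2816 + 0.8416)² / (ln 0.659)² = 103.7, so 104. With exponential PFS, 24 months' uniform accrual (A) and 12 months' follow-up (F), the event probability is 1 − [exp(−λF) − exp(−λ(A+F))]/(λA) = 0.990 for control and 0.961 for combination, mean 0.976. Then 104/0.976 = 106.6, and 106 patients give 103.4 events and 79.9% power. The stated 106 reproduces, so the exponential model with these medians fits the design.

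**Exposure.** Assume that treatment ends at progression and that there is no other discontinuation.

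- Progression rates: ln 2/2.9 = 0.239 and ln 2/4.4 = 0.158 per month.
- Mean time on treatment (1/rate): 4.18 vs 6.35 months, ratio 1.52.
- Adding 30 days (0.986 month): 5.17 vs 7.33 months, ratio 1.42. With 53 per arm this is about 274 vs 389 patient-months.

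**Crude percentages with no true difference.** With the same constant hazard h in both arms, P(at least one event) = 1 − exp(−0.986h) × λ/(λ + h). For h = 0.10, control is 1 − 0.906 × 0.239/0.339 = 36.1% and combination is 1 − 0.906 × 0.158/0.258 = 44.6%. The documents give no event rate for this trial, so h is an assumption shown over a range (differences from unrounded values):

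| h per month | Control | Combination | Difference |
|---|---|---|---|
| 0.05 | 21.3% | 27.7% | 6.5 points |
| 0.10 | 36.1% | 44.6% | 8.5 points |
| 0.20 | 55.3% | 63.8% | 8.5 points |

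Outside this middle range the gap narrows: 5% in control becomes 6.9%, and 80% becomes 85.2%. The ratio of percentages falls from 1.39 to 1.06 as events become common.

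**What shrinks or reverses it.**

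- Early onset: if events arise only in the first 2, 4 or 6 cycles, the exposure ratio is 1.06, 1.11 or 1.16. For h of 0.10 to 0.20 the excess with a 6-cycle limit is about 3 to 5 points; with a 2-cycle limit it is about 1 point or less.
- Carboplatin stopped after cycle 6: under the assumed medians about 52% of combination and 37% of control patients are progression-free at 18 weeks. If the combination arm's hazard halves from 126 days plus the 30-day tail, the excess falls to about 2 to 5 points. If it drops to zero, an extreme case, the sign reverses by about 2 to 4 points. The share who stop is not in the documents.
- Crossover events pooled with control: assuming 30% to 70% cross over with a median of 1.5 to 2.9 months on crossover treatment, the ratio of observed time runs from 1.26 down to 0.91.

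**With adjustment.** Under equal constant hazards the exposure-adjusted rate ratio is 1.00. A 12-week cumulative incidence with progression-related end of observation as a competing event leaves an excess of about 0.5 to 1.3 points with the 30-day tail, or 1.0 to 3.1 without it.

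**The case against.** A descriptive n (%) table is ordinary in a 106-patient phase II trial. Section 3 lists no safety objective, and the plan sets no safety test, margin or decision rule, so no planned inference is damaged. The excess computed above is 0.78 to 0.90 of one standard error at 53 per arm (standard error 8.3 to 9.5 points), less than the sampling noise. One can also compute the chance that the combination looks at least 10 points worse with no true difference: 34% to 44%, against 10% to 15% with equal exposure. That threshold appears nowhere in the plan, and the result should not carry weight.

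A reader might go further and infer that the plan reports plain event counts, and that the table will show excess toxicity for atezolizumab in the ratio 1.5 even if it adds none. The documents do not support this. Section 17.4 does not specify counts. The 1.5 applies to treatment time, not to observation time or patient percentages. The direction depends on a real PFS gain, on when events occur, on carboplatin use after cycle 6 and on where crossover events are counted. Nor does all surveillance end at 30 days, since AESIs are followed to year 3.

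These limits stand. What also stands is that the crude table cannot show which of these situations has arisen.

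**Conclusion.** The point holds as a conditional one. Section 17.4 makes no allowance for time at risk, and the design's own medians imply about 1.5 times the mean treatment time and 1.4 times the mean observation time in the combination arm. At an equal constant hazard, crude percentages could differ by up to about 6 to 9 points with no difference in toxicity. This rests on exponential PFS, treatment ending at progression, the assumed PFS gain being real, and control events being cut at crossover. Treatment past RECIST progression in the combination arm would lengthen its exposure further; the factors listed in the working would reduce the difference or change its sign. The primary analysis, its power and its type I error are untouched. This is a cheap improvement to the safety analysis, not a flaw in the trial's main conclusion.

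**What to change.** In Section 17.4, keep the crude n (%) table and add, by randomised arm with control cut at crossover:

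1. treatment duration;
2. exposure-adjusted incidence, as first events per patient-month from first dose to 30 days after last dose;
3. cumulative incidence of first Grade 3 or higher event (including Grade 5) and of first immune-mediated event, at one fixed time common to both arms (12 weeks, for example), treating progression-related end of observation as a competing event.

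Show crossover-period events in a separate table, and list separately any AESIs found at the 1- to 3-year follow-up. State that between-arm safety differences will be interpreted with these measures.

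The downsides should be stated too. The rate assumes a roughly constant hazard. The fixed-time estimate leaves out later immune-mediated events, and with progression as a competing event it removes most but not all of the exposure difference.

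The cost is SAP wording and a few hours of programming. Section 13.4 already has event start and end dates recorded, and no new visits or changes to treatment are involved.

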### 17.5 Reporting and Exclusions

All patients included in the study must be assessed for safety, tolerability, and response to treatment, even if there are major protocol treatment deviations or if they are ineligible. Each patient will be assigned one of the following categories: 1) complete response, 2) partial response, 3) stable disease, 4) progressive disease, 5) early death from malignant disease, 6) early death from toxicity, 7) early death because of other cause, or 9) unknown (not assessable, insufficient data).

All of the patients who met the eligibility criteria and received study drugs for 4 weeks should be included in the main analysis of the clinical benefit rate. Patients in response categories 4-9 should be considered to have a treatment failure (disease progression). Thus, an incorrect treatment schedule or drug administration does not result in exclusion from the analysis of the response and clinical benefit rate.

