Upon satisfactory review of eligibility documents submitted, the Coordinating Center will approve enrollment and issue a subject ID number if one was not issued at screening. Once registration/enrollment confirmation from Coordinating Center is received, the site may proceed with protocol procedures.

Please contact the assigned Study Contact with any questions regarding this process. You can also reach out to your assigned CRA once the study is activated.

The VICC Coordinating Center will assign sequence numbers to all patients in screening. Only patients deemed eligible will be randomized to a treatment arm. Sequence numbers will only be re-used if a patient screen fails and then re-screens. The Coordinating Center will randomize eligible patients to carboplatin + atezolizumab or carboplatin alone. Following registration and randomization, eligible participants should begin protocol treatment within 1 week. Issues that would cause treatment delays should be discussed with the Protocol Chair. If a participant does not receive protocol therapy following randomization within allowed time period, the participant will become ineligible and will not be enrolled on study. Such patients will have to undergo screening again to participate in the study in the future. Any requests for eligibility exceptions and/or deviations must be approved in writing by the Protocol Chair, as well as any committees required by local

institutional policies. As is generally accepted, standard of care procedures performed prior to consent, but within the protocol defined screening window for each assessment can be used for study purposes. All research only procedures must be performed after the consent date.

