- i Tumor assessment should be performed approximately every 3 cycles (up to -5 days) while on study treatment (i.e. on or up to 5 days prior to Day 1 of Cycles 4, 7, 10 etc) and at End-of-treatment visit if not obtained within the past 6 weeks. Scans should consist of CT scan of the chest, abdomen, and pelvis and a bone scan at baseline. Of note, if the prior bone scan did not show metastases, it does not need to be repeated if the bone scan was obtained within 8 weeks of CID1. Subsequent scans should consist of CT chest, abdomen and pelvis, and bone scan if bone metastases were present on the baseline studies. MRI is also an acceptable form of imaging. At the end of treatment, all scans (baseline and through disease progression) should be sent on a CD to the Vanderbilt Cancer Imaging Support Laboratory for central review and assessment. See Section 12.6 for details and address.
- j Archived tumor biopsy specimen: Archived biopsy block (unstained slides) will be requested at the time of registration prior to initiation of treatment. See Section 11.1 for details. If archived tissue is not available, the VICC coordinating center should be contacted.
- k After signing consent, a fresh tumor biopsy from a metastatic site amenable to a reasonably safe biopsy will be obtained prior to day 1 and upon progression of disease (see Section 11). The second biopsy will not be required for patients who are removed from study for reasons other than disease progression. A patient who undergoes a research biopsy procedure for the purpose of this protocol, in whom inadequate tissue is obtained, is not obligated to undergo a repeat biopsy.

- l After cycle 6, at the discretion of the treating physician, carboplatin can be stopped and atezolizumab can be continued as a single agent.
- m The dose of steroids before each carboplatin injection should be recorded. Prohibited medications (section 8) must be discontinued at least 7 days prior to initiation of study drug (C1D1).
- n 1, 2, and 3 year follow-up can be done by phone or chart review to document survival status, and if applicable, the date of death and cause of death. Surveillance for Adverse Events of Special Interest (AESIs) (see section 13.5.12) should be included.
- o Biopsy questionnaire should be filled out by the patient on C2D1. Form can be found in the packet of supplemental forms.  

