### **8.7 Criteria for Removal from Study**

Patients will be removed from study when any of the criteria listed below apply. All patients who initiate protocol treatment will be included in the overall evaluation of response (intent-to-treat analysis). All reasons for discontinuation of therapy should be documented clearly in the medical record.

If a subject discontinues or withdraws from the study, every reasonable attempt will be made to get a tissue/tumor biopsy, along with blood, at the end of treatment, if the subject is able and willing.

Patients may be withdrawn from the study if they experience any of the following:

- Disease progression, per investigator assessment by RECIST (or irRECIST for atezolizumab arm)
- Intolerable toxicity to atezolizumab or carboplatin. Patients assigned to carboplatin + atezolizumab who experience toxicity to atezolizumab or carboplatin can continue on study with single agent carboplatin or atezolizumab, respectively, at the discretion of the treating physician. Patients will be followed for disease progression and should continue radiologic assessments every 3 cycles as per the study.

Other reasons for patient discontinuation may include, but are not limited to, the following:

- Non-compliance with the study protocol, including, but not limited to not attending the majority of scheduled visits. The Protocol Chair will determine when non-compliance should lead to removal from study. Note: The patients will still be included in the overall evaluation of response (intent-to-treat analysis).
- Patient personal decision. The reason for discontinuation from the study must be documented. The patients will be included in the overall evaluation of response (intent-to-treat analysis) if any protocol therapy was administered prior to withdrawal.
- If the patient becomes pregnant
- Patient is lost to follow-up
- Study is terminated for any reason

The investigator has the right to discontinue a patient from the study for any medical condition that the investigator determines may jeopardize the patient's safety if he or she continues in the study; for reasons of noncompliance (e.g., missed doses, visits); or if the investigator determines it is in the best interest of the patient. The Protocol Chair should be notified in such cases.

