## 12.1 Definitions

Evaluable for toxicity. All patients will be evaluable for toxicity from the time of their first treatment with atezolizumab and/or carboplatin. Evaluable for objective response. Only those patients who have measurable disease present at baseline, have received at least one cycle of therapy, and have had their disease re-evaluated will be considered evaluable for response. These patients will have their response classified according to the definitions stated below. (Note: Patients who exhibit objective disease progression prior to the end of cycle 1 will also be considered evaluable.)

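### The main clinical benefit rate analysis is limited to eligible patients with 4 weeks of drug, which can drop early failures and conflicts with section 8.7

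*Combined protocol and SAP*

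**What the plan says.** Three sections define who counts when response is evaluated, and they differ.

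- **Section 17.5 (Reporting and Exclusions)**, on CBR: "All of the patients who met the eligibility criteria and received study drugs for 4 weeks should be included in the main analysis". The same paragraph adds: "Patients in response categories 4-9 should be considered to have a treatment failure (disease progression"). Those categories include three kinds of early death and the unknown category. The preceding paragraph requires response to be assessed in every patient, ineligible ones included.
- **Section 8.7 (Criteria for Removal from Study)**: "All patients who initiate protocol treatment will be included in the overall evaluation of response (intent-to-treat analysis"). On patients who leave by personal decision: "The patients will be included in the overall evaluation of response (intent-to-treat analysis) if any protocol therapy was administered prior to withdrawal".
- **Section 12.1 (Definitions)**, for objective response, gives this rule: "Only those patients who have measurable disease present at baseline, have received at least one cycle of therapy, and have had their disease re-evaluated" are evaluable, with one addition: "Patients who exhibit objective disease progression prior to the end of cycle 1 will also be considered evaluable".

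Section 6.1 says of a patient who is randomised but not treated within the allowed window that "the participant will become ineligible and will not be enrolled on study". Section 3.2 makes CBR a secondary endpoint (CR, PR, or SD for 6 months), and section 17.3 reports it with a 95% confidence interval. No section says which patient set governs CBR.

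**The concern.** Receiving 4 weeks of drug is a post-randomisation outcome. Patients who miss it are mostly those who died, stopped for toxicity or withdrew, and almost none of them can show benefit. Removing them shrinks the denominator and leaves the numerator nearly intact, so CBR rises. If the arms lose different numbers, the comparison is biased as well. The trial is open-label and its stopping rules differ by arm: under sections 8.4 and 8.7 a combination patient who stops one drug for toxicity may continue on the other, an option the carboplatin-alone arm lacks. Added toxicity from the combination could act the opposite way, so the documents do not show a direction.

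Section 17.5 is also inconsistent within itself. It makes early death a failure, yet a patient who dies before week 4 does not meet the condition for the set in which failures are counted. Four weeks of drug is undefined on a 21-day cycle: it could mean time on treatment or receipt of a second dose.

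**Working it through.** **1. Who is counted under each section**

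| Patient | 8.7 | 17.5 main CBR set | 12.1 evaluable set |
|---|---|---|---|
| One dose, withdraws, no repeat scan | in | out | out |
| Treated, dies in week 3, no documented progression | in | out, though classed as a failure | out |
| Objective progression before end of cycle 1, drug stopped | in | out | in |
| Treated for months, later found ineligible | in | out | in if re-evaluated |
| Randomised, never treated | out | out | out |

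The first four rows show the conflict. The last shows that no set is based on all randomised patients.

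**2. The plan's own figure.** Section 17.2 gives N = 106 (53 per arm), medians 2.9 and 4.4 months, one-sided 0.10, 80% power, 24 months of accrual and 12 of follow-up.

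- HR = 2.9/4.4 = 0.659. Events (Schoenfeld) = 4(1.282 + 0.842)²/(ln 0.659)² = 104.
- Event probability = 1 − [exp(−12λ) − exp(−36λ)]/(24λ), with λ = ln 2/median: 0.990 and 0.961, mean 0.976.
- N = 104/0.9755 = 106.6; power at N = 106 is 79.9%.

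The sample size reproduces and is not in question. The plan gives no expected CBR by arm and no rate of early stopping.

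**3. Illustration from the design medians.** Assumptions: exponential PFS; PFS beyond 6 months stands in for CBR. The proxy is imperfect, because a responder who progresses before 6 months may still count.

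- 4 weeks = 28/30.4375 = 0.92 months.
- PFS event by 4 weeks: 1 − 2^(−0.92/2.9) = 0.197 (10.5 of 53); 1 − 2^(−0.92/4.4) = 0.135 (7.2 of 53).
- PFS beyond 6 months: 2^(−6/2.9) = 0.238 (12.63 of 53); 2^(−6/4.4) = 0.389 (20.60 of 53).

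If a share f of the early events is excluded, the rates are 0.238/(1 − 0.197f) and 0.389/(1 − 0.135f):

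| f | Carboplatin | Combination | Difference (points) |
|---|---|---|---|
| 0 | 23.8% | 38.9% | 15.0 |
| 0.1 | 24.3% | 39.4% | 15.1 |
| 0.5 | 26.4% | 41.7% | 15.2 |
| 1 | 29.7% | 44.9% | 15.2 |

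The ratio falls from 1.63 at f = 0 to 1.51 at f = 1. The true f is unknown. The first on-treatment scan is due "on or up to 5 days prior to Day 1 of Cycles 4, 7, 10 etc", so about week 9, and many early PFS events would be undetected with the patient still on drug. Toxicity stops, withdrawals and ineligible patients come on top.

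**4. Illustration with assumed counts of excluded failures**

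| Excluded (carboplatin, combination) | Carboplatin | Combination | Difference (points) |
|---|---|---|---|
| 5, 5 | 12.63/48 = 26.3% | 20.60/48 = 42.9% | 16.6 |
| 2, 6 | 12.63/51 = 24.8% | 20.60/47 = 43.8% | 19.1 |
| 6, 2 | 12.63/47 = 26.9% | 20.60/51 = 40.4% | 13.5 |

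With no true difference (13/53 = 24.5% in each arm), dropping 2 failures from one arm and 8 from the other gives 13/51 = 25.5% against 13/45 = 28.9%, a spurious gap of 3.4 points.

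**The case against.** The best defence is that section 17.5 says who should be included and never says that others are removed. The text around it points towards counting early failures: ineligible patients must still be assessed, early death and unknown have their own categories, and those categories are failures. Section 8.7 does not name CBR, so the two sections could be read as covering different analyses. The likely effect is also small. At f = 0.1 the rise is about 0.5 points per arm, and even the extreme 6-point rise lies inside the approximate 95% half-width for 53 patients (1.96 × √(0.238 × 0.762/53) = 11.5 points; 1.96 × √(0.389 × 0.611/53) = 13.1 points). The larger shifts in the difference come from assumed unequal counts.

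The points on size stand, and they limit how serious this is. The reading of the text does not. If everyone counts, the eligibility and 4-week conditions have no function, and the section is headed as dealing with exclusions. The closing sentence of 17.5 protects only against exclusion for schedule or administration errors, not for early death, withdrawal or ineligibility. CBR is built from the same response categories that 8.7 covers. That imprecision exceeds the bias does not excuse an undefined denominator.

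It is also fair to say that sections 12.1 and 6.1 raise neighbouring questions. Section 12.1 concerns objective response and expressly keeps early objective progression. The status of randomised but untreated patients under 6.1 reaches beyond CBR, to every endpoint.

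**Conclusion.** The concern holds. As written, the main CBR set carries an eligibility condition and a post-randomisation exposure condition. It conflicts with the all-treated rule in 8.7 and with the failure rule in its own paragraph. Following 17.5 can inflate CBR in both arms; the repeat-assessment condition in 12.1 can do the same to ORR.

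The size cannot be established from the documents. In the design-median illustration the rise is from about 0.5 points per arm (10% of early events excluded) to about 6 (all excluded), with the between-arm difference steady at 15.0 to 15.2 points. With assumed unequal exclusions the difference ranged from 13.5 to 19.1 points, so the bias could run either way. CBR is secondary with no planned power, and the 4-week rule does not affect the primary PFS test or N = 106. This should be corrected, but it does not threaten the main result.

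**What to change.** In section 17.5, make all randomised patients, or at minimum all treated patients as in 8.7, the denominator for the main CBR and ORR in both arms. Count early death, early stop without documented benefit, no repeat assessment and unknown as non-response. Keep the eligible 4-week set and the section 12.1 evaluable set as sensitivity analyses, state what 4 weeks of drug means, and report the number excluded and the reason by arm. Align 6.1, 8.7, 12.1 and 17.5 to that one definition. If all randomised patients are used, add a line on how a patient who is randomised, not treated and later re-screened is counted.

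The cost is a wording amendment to those four sections, with IRB approval at each institution (section 15.1). No extra patients or assessments are needed, because untreated or unassessed patients count as non-responders. Wherever the narrower sets would have excluded failures, the reported CBR and ORR will be somewhat lower.
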